### **3.0 Patient Eligibility**

#### 3.1 Inclusion Criteria

- 3.1.1 Laboratory confirmed SARS-CoV-2 infection
- 3.1.2 Admitted to hospital for management of SARS-CoV-2
- 3.1.3 Age  $\geq 18$
- 3.1.4 Subject or legal representative able to give informed consent
- 3.1.5 Ability to take all study drugs
- 3.1.6 Respiratory status of 3 or greater on the WHO ordinal scale
- 3.1.7 ALT or AST  $\leq 5 \times$  ULN
- 3.1.8 Creatinine clearance  $\geq 50$  mL/min using the Cockcroft-Gault formula
- 3.1.9 Willingness to provide mandatory specimens for correlative research and banking (see Section 6.0 and 9.0).

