## 5.0 Stratification Factors

- 5.1 Age:  $\geq 65$  vs.  $< 65$  years
- 5.2 Clinical status ordinal score at enrollment: 3-4 (hospitalized with mild disease) vs. Score 5 (hospitalized with severe disease)

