## 12.0 Treatment Evaluation Criteria

The ordinal scale used for assessment of the clinical and respiratory status on each day of the study is included below. Each day, the worst (i.e., highest ordinal) score from the previous day will be recorded, i.e., on Day 3, the highest ordinal score from Day 2 is obtained and recorded for Day 2. The scale is as defined by the WHO as follows:

Patient State	Descriptor	Score
Uninfected	No Clinical or Virological Evidence of Infection	0
Ambulatory	No Limitation of activities	1
	Limitation of activities	2
Hospitalized, Mild Disease	Hospitalized, no oxygen therapy	3
	Oxygen by mask or nasal prongs	4
Hospitalized, Severe Disease	Non-invasive ventilation or high flow oxygen	5
	Intubation and Mechanical Ventilation	6
	Ventilation + additional organ support-pressors, RRT, ECMO	7
Dead	Death	8

In addition, patients will be stratified at baseline based on the ordinal scale below. A score of 3-4 is associated with hospitalized with mild disease versus score of 5 is associated with severe disease.

The primary outcome assessment for efficacy will be evaluated based on the number of patients who are alive AND respiratory failure-free at Day 28 after study entry.

Respiratory failure at Day 28 will be defined by clinical diagnosis of respiratory failure corresponding to a score of 5-8 on the above ordinal scale at Day 28. Specifically, respiratory failure is defined by meeting any of the following criteria:

- Requiring ICU admission,
- mechanical ventilation,
- ECMO,
- non-invasive ventilation,
- or high flow oxygen devices,

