#### 13.3.2 Secondary Endpoints

1. Proportion of patients alive AND free of ventilator use or ECMO at Day 28: The proportion will be evaluated based on the number of patients who are alive AND free of ventilator use or ECMO (clinical status score of 5 or less) at Day 28 after study entry divided by the number of total patients enrolled for each treatment arm.

2. Time to death: Time to death will be measured as the number of days from the date of randomization/study entry until death date. Deaths due to any cause will be considered an

event. All-cause mortality rate at 28 and 56 days after study entry will be evaluated. If the patient is lost to follow-up or withdraws from the study early, or doesn't experience a death event, they will be censored at Day 28.

**3. Time to clinical improvement:** Clinical improvement will be defined as a 2 or more point decrease on the WHO ordinal scale (see Section 12.0). Time to clinical improvement will be calculated as the number of days from study entry until the earliest date of clinical improvement as defined above. The number of patients who achieve clinical improvement by Day 14 and 28 will be evaluated. In addition, time to clinical improvement will also be assessed.

**4. Clinical status at Days 14 and 28:** Evaluation of the distribution of clinical status scores by the ordinal scale will be done at days 14 and 28.

**5. Length of Hospitalization Stay:** This will be defined as the time from randomization/study entry until the time of hospital discharge. Time in the ICU will be described in number of days spent receiving ICU care, if applicable.

**6. Duration of Mechanical ventilation / ECMO:** Ventilator / ECMO days will be defined as the number of days where the clinical status score is equal to 6 or 7 for those subjects who have a baseline score of 6-7 at study entry. Total number of days will be the sum of all reported days, regardless of whether the days occur consecutively or in disjoint intervals.

**7. Duration of non-invasive ventilation / high-flow oxygen:** Non-invasive ventilation / high-flow oxygen days will be defined as the number of days where the clinical status score is equal to 5 for those with a baseline score of 5 at study entry. Total number of days will be the sum of all reported days, regardless of whether the days occur consecutively or in disjoint intervals.

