#### 13.5 Secondary Analyses

1. Proportion of patients alive AND free of ventilator use / ECMO at Day 28: The proportion will be evaluated based on the number of patients who are alive AND free of

ventilator use or ECMO at Day 28 after study entry divided by the number of total patients enrolled for each treatment arm. The proportion of patients who have this event will be analyzed similarly to the primary endpoint. Comparisons will be done by use of independent samples Z-test for proportions and a 95% confidence interval will be constructed for the difference between groups. The Cochran-Mantel-Haenszel test will be used to include stratification factors. Multivariable logistic regression models will be used to assess the influence of treatment arm on while adjusting for other factors of interest.

**2. Time to death and Mortality rate:** The Kaplan-Meier method will be used evaluate differences in the distributions of time-to-death between treatment arms. Rates of mortality at day 28 and day 56 mortality will be estimated. Patients lost to follow-up or who withdraw early will be considered censored at their last assessment date for the Day 28 rate. The stratified log-rank test will be used to compare differences in distributions of time to death based on stratification factors. Cox proportional hazards model will be used to compare treatment arms with inclusion of stratification factors or adjustment for covariates of interest.

**3. Time to clinical improvement:** Time to clinical improvement will be evaluated using Kaplan-Meier methods and Cox regression models. Rates of clinical improvement at days 14 and 28 will be estimated. Time to clinical improvement will be assessed after all patients have reached day 14 and 28; no clinical improvement at day 14 or 28 or death before day 14 or 28 will be considered as right censored. Hazard ratios with 95% confidence intervals will be calculated by the Cox proportional-hazards model. Covariates of interest will be included in regression models.

**4. Clinical status at Days 14 and 28:** The distribution of the clinical status will be summarized by arm at days 14 and 28. A proportional odds model with treatment arm and disease severity at baseline as covariates will be used to evaluate whether the odds of improvement on the ordinal scale are higher for the treatment arm as compared to control.

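### Time to clinical improvement: death is right censored with no censoring date given, and censoring at the date of death would overstate the improvement rate, more so in the arm with more deaths

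*Combined protocol and SAP*

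**What the plan says.** Section 13.3.2 item 3 defines the event: "Clinical improvement will be defined as a 2 or more point decrease on the WHO ordinal scale". The time is "calculated as the number of days from study entry until the earliest date of clinical improvement as defined above". The same item also calls for the number of patients improved by Days 14 and 28.

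Section 13.5 item 3 specifies Kaplan-Meier estimates, improvement rates at Days 14 and 28, and Cox hazard ratios. Its censoring rule is: "no clinical improvement at day 14 or 28 or death before day 14 or 28 will be considered as right censored". It names no competing-risk method and does not say at what time a death is censored.

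The Missing Data Considerations that follow in 13.5 give a censoring time for time-to-event outcomes, the last observed assessment. That rule covers only patients lost to follow-up or withdrawn.

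Eligibility in section 3.1 starts at "Respiratory status of 3 or greater on the WHO ordinal scale".

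**The concern.** Death before improvement is not ordinary censoring, because the patient can no longer improve. A Kaplan-Meier estimate that removes such a patient from the risk set at death gives them the later improvement chances of those still at risk. It therefore estimates improvement in a population where nobody dies, and one minus Kaplan-Meier exceeds the share of patients who actually improved. The excess is larger where there are more deaths.

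Objective 2.2.3 asks whether camostat shortens time to improvement, and this analysis answers it. If the arms differ in mortality, the curves and the Day 14 and Day 28 rates would show less of that difference than the patients experienced. The same data also give different rates and hazard ratios according to the censoring date chosen, so the date should be fixed before unblinding.

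**Working it through.** The plan gives no improvement rate, so there is no figure of its own to reproduce for this endpoint. The 132 patients per arm in section 13.6 were sized on the primary endpoint.

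**Inputs.** Day 28 mortality D: 8.0% and 11.6%, the remdesivir and placebo figures in the Background, used only as an illustrative range. True share improved by Day 28, I: 60%, 70% and 80% (assumed). Constant hazards of improvement and death over 28 days (assumed).

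**Formula.** The total hazard over 28 days is −ln(1 − I − D), of which the fraction I/(I + D) belongs to improvement. With deaths censored at the date of death,

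1 − KM(28) = 1 − (1 − I − D)^(I/(I + D)).

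For I = 0.70 and D = 0.116: 1 − 0.184^(0.70/0.816) = 0.766, an excess of 6.6 points.

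| True improved | Deaths | 1 − KM | Excess (points) |
|---|---|---|---|
| 60% | 8.0% | 63.4% | 3.4 |
| 70% | 8.0% | 74.3% | 4.3 |
| 80% | 8.0% | 85.4% | 5.4 |
| 60% | 11.6% | 65.2% | 5.2 |
| 70% | 11.6% | 76.6% | 6.6 |
| 80% | 11.6% | 88.5% | 8.5 |

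**Check by simulation** (200,000 patients, I = 70%, D = 11.6%): censoring at death gives 76.5%; keeping deaths unimproved to Day 28 gives 70.0%, the true share.

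**Dependence on mortality.** Hold the improvement hazard at ln 2/11 per day (assumed median 11 days). Then 1 − KM at Day 28 is 1 − exp(−28 × ln 2/11) = 82.9% whatever the mortality. The share that truly improves is 77.7% with 8% deaths, 75.3% with 11.6% and 72.4% with 16%.

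**Two arms of 132** (assumed counts):

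- Arm A, 15 deaths and 92 improved: true 92/132 = 69.7%. With I + D = 107/132, 1 − KM = 1 − (25/132)^(92/107) = 76.1%.
- Arm B, 25 deaths and 86 improved: true 86/132 = 65.2%. With I + D = 111/132, 1 − KM = 1 − (21/132)^(86/111) = 75.9%.

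A true deficit of 4.5 points in arm B appears as about 0.2. Replacing constant hazards by gamma-distributed times (shape 1.5 to 4, mean death at Day 8 or 12, mean improvement at Day 8 or 11), the apparent result for arm B ran from a 1.9-point deficit to a 0.9-point advantage. More than half of the true difference was lost in every setting. With deaths kept to Day 28, the estimates are 69.7% and 65.2%, as they should be.

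**The score-3 case.** On the scale in section 12.0, score 3 is "Hospitalized, no oxygen therapy" and score 2 is ambulatory with "Limitation of activities". Going from 4 to 2 or from 5 to 3 is two points. Going from 3 to 2 is one, so a score-3 patient sent home with limitations has not improved until reaching score 1 or 0. If 10% to 30% of the 264 enter at score 3 and 25% to 75% of those go home with limitations (both assumed), this concerns 264 × 0.10 × 0.25 = 6.6 to 264 × 0.30 × 0.75 = 59.4 patients, or about 7 to 59.

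**The case against.** The strongest reply is that the plan does not say deaths are censored at the date of death. Section 13.5 item 3 assesses the endpoint once all patients have reached Days 14 and 28, and puts non-improvement at those days and earlier death in one clause. That can be read as censoring both at the Day 14 or Day 28 horizon, in which case the bias disappears. This stands, and it limits the point to an unstated date whose usual reading is harmful. It does not remove the need to state the date.

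Second, a Cox model with death censored estimates a cause-specific hazard ratio, a recognised quantity. That also stands: the inflation computed here is in the Kaplan-Meier rate, and the choice of hazard ratio is a choice of estimand.

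Third, the report would contain other evidence. The count improved by Days 14 and 28, taken over all patients, treats the dead as not improved. Mortality has its own analysis, death is score 8 in the ordinal model, and length of stay covers discharge. A mortality difference would not vanish from the report, though it would be muted in the analysis that answers objective 2.2.3.

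A reader might infer that the plan makes a harmful arm look better. The documents do not support that. In the example above, the reversal needs 86 improved among 107 survivors (80.4%) in arm B against 92 among 117 (78.6%) in arm A, and 25/132 = 18.9% mortality. It disappears with 85 improved, with deaths around Day 12, or with constant hazards.

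A reader might also call the 2-point definition an error for score-3 patients. It is explicit, applies equally to both arms, and still counts a later fall to 1 or 0. Adding live discharge would not give the event one meaning at every baseline score either, since a score-5 patient still in hospital at score 3 would count as improved as before.

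**Conclusion.** The point holds as a gap in the specification. The plan right-censors death in a Kaplan-Meier and Cox analysis, gives no date for it and names no competing-risk method. On the usual reading, the Day 28 improvement rate is overstated by about 3 to 9 points at 8.0% to 11.6% mortality, given the assumed 60% to 80% true improvement and constant hazards. The overstatement is larger in the arm with more deaths, so a true deficit there is reduced or hidden; reversal occurs only under particular assumed inputs. On the horizon reading there is no such bias, which is why the date must be written down.

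The score-3 gap is correct arithmetic, but its size rests wholly on assumed shares and no bias between arms follows from it. It supports an optional sensitivity analysis only. The matter is confined to one secondary endpoint.

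**What to change.** In 13.5 item 3, replace the death clause with one of these:

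- Patients who die without improvement remain in the risk set as unimproved and are censored at Day 28 (Day 14 for the Day 14 rate).
- Improvement is reported as cumulative incidence with death as a competing event, compared by Gray's test or a Fine-Gray model.

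In either case, keep the cause-specific Cox hazard ratio as supportive, and leave the existing rule for loss to follow-up and withdrawal as it is.

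Optionally, add a sensitivity analysis that counts either a fall of 2 or more points or live discharge as improvement, with the pre-specified 2-point definition remaining the main one.

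The cost is a short wording change. Death and discharge dates are already needed for time to death and length of stay, so no new data are required, and the endpoint definition in 13.3.2 is untouched. The small downside is that a subdistribution hazard ratio has a different interpretation from the cause-specific one and must be labelled as such.

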### 2.2 Secondary Objectives include the following:

- 2.2.1 To determine if reduction in TMPRSS2 activity via direct inhibition with Camostat mesilate combined with SOC treatment will increase the proportion of patients alive and free of ventilator use or ECMO at Day 28 as compared to SOC treatment combined with placebo.
- 2.2.2 To determine if the combination of Camostat mesilate combined with SOC treatment will result in a decreased mortality rate at 28 and 56 days as compared to SOC treatment combined with placebo.
- 2.2.3 To determine if time to clinical improvement is reduced in patients receiving SOC treatment combined with Camostat mesilate as compared to SOC treatment combined with placebo.
- 2.2.4 To determine if Camostat mesilate combined with SOC treatment is associated with overall improved clinical status at Days 14 and 28 as compared to SOC treatment combined with placebo.
- 2.2.5 To determine if Camostat mesilate combined with SOC treatment is associated with a reduced length of stay in the hospital as compared to SOC treatment combined with placebo.
- 2.2.6 To determine if Camostat mesilate combined with SOC treatment is associated with reduced duration of:
  - a) mechanical ventilation or ECMO use,
  - b) non-invasive ventilation or high-flow oxygen use, and

- c) supplemental oxygen use as compared to SOC treatment combined with placebo.
- 2.2.7 To compare the safety and toxicity profile of Camostat mesilate combined with SOC treatment as compared to SOC treatment combined with placebo.
- 2.2.8 To determine if treatment with Camostat mesilate combined with SOC treatment is associated with decreased incidence of thrombotic events and bleeding complications as compared to SOC treatment combined with placebo.

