**8. Days of supplemental oxygen use:** Oxygen days will be defined as the number of days where the clinical status score is equal to 4-7 for those who have a clinical status score greater than or equal to 4 at study entry. Total number of days will be the sum of all reported days, regardless of whether the days occur consecutively or in disjoint intervals.

**9. Occurrence of adverse events related to treatment:** Adverse Events will be recorded and graded according to CTCAE version 5.0 criteria. Occurrence of grade 3 or higher adverse events and SAEs will be assessed between arms.

**10. Development of thrombosis / bleeding complications:** Incidence of arterial and venous thrombosis or bleeding complications will be described in both treatment groups.

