**5. Length of Stay:** Length of stay will be defined as the time from study entry until the time of hospital discharge and the number of days hospitalized will be compared between groups by use of non-parametric Wilcoxon rank-sum test. The proportions of patients who require an ICU admission will be compared between randomized groups by the use of independent samples Z-test for proportions and a 95% confidence interval will be constructed for the difference between groups. In addition, time in the ICU will be described in number of days spent receiving ICU care, if applicable.

**6. Duration of Mechanical ventilation / ECMO:** Duration of ventilator / ECMO use will be summarized by medians or quartiles by arm for those subjects who have a baseline score of 6-7 at study entry.

**7. Duration of non-invasive ventilation / high-flow oxygen:** Duration of non-invasive ventilation / high-flow oxygen will be summarized by medians and quartiles by arm for those patients who have a clinical status score of 5 at study entry.

**8. Duration of supplemental oxygen use:** Duration of supplemental oxygenation use will be summarized by medians and quartiles by arm for those patients who have a clinical status score greater than or equal to 4 at study entry.

**9. Occurrence of adverse events related to treatment:** Analyses for safety will include all participants who are randomized and received at least 1 dose of study treatment.

Participants will be grouped according to the treatment to which they were randomized. Events will be summarized on the basis of the date of onset for the event. The maximum grade for each type of adverse event will be recorded for each patient. Frequency tables of adverse events will be constructed based on maximum grade for each treatment arm. Overall adverse event rates, rates of grade 3 or higher events and serious adverse events will be compared between treatment groups using Chi-square or Fisher's exact test.

**10. Development of thrombosis / bleeding complications:** Incidence of arterial and venous thrombosis or bleeding complications will be described and compared by treatment arms by use of chi-square or Fisher's exact test.

Subgroup analyses for the primary and secondary analyses will examine the treatment effect across the following subgroups of interest. Forest plots with odds ratio and 95% confidence intervals will be presented along with interaction tests.

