#### Missing Data Considerations

All efforts will be made to minimize the occurrence of missing data. Subjects who discontinue treatment in either arm will be encouraged to remain in the study and to continue with follow-up visits for key outcomes at Day 28 and 56.

For time to event outcomes, subjects who are lost to follow-up or withdrawal from the study prior to Day 28 and prior to observing/experiencing the event will be censored at the time of their last observed assessment.

For duration of non-invasive ventilation/high-flow oxygen, ventilation/ECMO or supplemental oxygen, subjects will be considered to have the event of interest until Day

28 if they have the event of interest at their last follow-up assessment day before Day 28 in the case of lost to follow-up or patient withdrawal. Likewise, if they do not have the event of interest at their last follow-up assessment, they will be considered to not have this event through Day 28.

If the subject is discharged and no further hospitalization data are available, then the subject will be assumed to not have been readmitted to the hospital.

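### Intubation or death shortens the high-flow/NIV duration (13.3.2, item 7), so its by-arm median for objective 2.2.6 can favour the arm that deteriorates more

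*Combined protocol and SAP*

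**What the plan says.** Objective 2.2.6 reads: "To determine if Camostat mesilate combined with SOC treatment is associated with reduced duration of" three kinds of support, so a shorter duration is the hoped-for result. Section 13.3.2 defines the measures:

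- Item 7 (non-invasive ventilation or high-flow oxygen): days on which the "clinical status score is equal to 5 for those with a baseline score of 5 at study entry".
- Item 6 (mechanical ventilation or ECMO): days on which the "clinical status score is equal to 6 or 7 for those subjects who have a baseline score of 6-7 at study entry".
- Item 8 (supplemental oxygen): days on which the "clinical status score is equal to 4-7 for those who have a clinical status score greater than or equal to 4 at study entry".

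In each item the days are added up "regardless of whether the days occur consecutively or in disjoint intervals". On the scale in section 12.0, intubation is 6, ventilation with further organ support is 7 and death is 8. The worst score of each day is the one recorded.

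The analysis in section 13.5 is descriptive. For item 7: "Duration of non-invasive ventilation / high-flow oxygen will be summarized by medians and quartiles by arm". Items 6 and 8 are handled alike, with no test.

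The Missing Data Considerations carry support forward to Day 28 for patients lost or withdrawn while on it. The converse also applies, again up to Day 28: "if they do not have the event of interest at their last follow-up assessment, they will be considered to not have this event". Neither rule mentions death or escalation.

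**The concern.** A count of days at exactly score 5 falls when a patient recovers, and it falls equally when the patient is intubated or dies. With recovery unchanged, an arm with more intubations or deaths therefore accumulates fewer item 7 days and can show the shorter median. The by-arm medians and quartiles are the only analysis of objective 2.2.6, so nothing within that objective corrects the reading. A drug that prevents deterioration could look worse on it, and a harmful drug could look better.

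**Working it through.** The plan gives no figure for these durations, so there is none to reproduce. The first step uses the definitions alone. The hazards in the later steps are all assumptions, because the documents state none.

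**1. Definitions, patient by patient.** Take a baseline-5 patient at score 5 on Days 1 to 3, followed to Day 28.

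| From Day 4 | Item 7 | Item 8 |
|---|---|---|
| Improves to score 4 | 3 | 3 + later days at score 4 |
| Dies | 3 | 3 |
| Ventilated through Day 28 | 3 | 3 + 25 = 28 |
| Lost after Day 3, last seen at score 5 | 3 + 25 = 28 | 28 |
| Intubated on Day 4, then lost | 3 | 28 |

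Item 7 gives recovery, death and prolonged ventilation the same value. A patient lost while at score 5 gets the maximum. One intubated and then lost counts as free of the item 7 event. If a ventilated patient returns to score 5, the count resumes. In item 8 ventilated days count, so death is the only worsening that cuts it short. The same holds for item 6 in its own baseline group.

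**2. Item 7, intubation final.** With recovery r and escalation or death e per day, the median is ln 2/(r + e). Take r = 0.10 in both arms and e = 0.05 on control vs 0.025 on drug.
- Control: 0.693/0.15 = 4.6 days. Drug: 0.693/0.125 = 5.5 days.
- The medians tie when r' + 0.025 = 0.15, so r' = 0.125, which is 25% more recovery on drug.

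**3. Item 7, with return to score 5.** The e of step 2 is split into 90% intubation and 10% death. From score 5: recovery 0.10; intubation 0.045 vs 0.0225; death 0.005 vs 0.0025. From the ventilator: back to score 5 at 0.04; death 0.03. Time at score 5 to Day 28 was computed by forward recursion in steps of 0.02 day.
- Medians 5.3 control vs 6.0 drug; means 7.3 vs 8.2; Day 28 mortality 14.0% vs 7.8%.
- The medians tie at about 15% more recovery on drug.
- In whole days the control probability of at most 5 days is 0.501. The control median is then 5 or 6 depending on how days are counted, and the arms can tie at 6.
- With faster extubation (0.15/day): medians 6.1 vs 6.5, tie at about 7%.
- Over r from 0.06 to 0.15 and e from 0.03 to 0.08 (halved by the drug), the tie point runs from about 6% to 41%.

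**4. Item 6, death only.** Off support 0.06/day in both arms; death 0.04 vs 0.02.
- ln 2/0.10 = 6.9 vs ln 2/0.08 = 8.7 days. Tie at 0.02/0.06 = 33% more recovery.

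**5. Item 8 under the step 3 hazards.** Add a score-4 stage with an assumed off-oxygen rate.

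| Off-oxygen rate per day | Median, control vs drug |
|---|---|
| 0.10 | 16.3 vs 16.5 |
| 0.15 | 13.8 vs 13.8 |
| 0.25 | 11.4 vs 11.3 |
| 0.50 | 9.4 vs 9.2 |

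These are simulated and accurate to about 0.1 day. The medians are about equal, because the longer ventilation in the worse arm offsets its earlier deaths.

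**The case against.** The strongest reply is that little depends on these items. They carry no test and no decision. The same deaths and intubations count against an arm in the primary endpoint (scores 5 to 8 are failures), the ventilator/ECMO-free proportion, mortality and ordinal status. A reader would see excess deaths beside a shorter median. Item 6 may also have few patients, since the severity strata in section 5.2 stop at score 5. All of this stands and limits the weight of the point. It does not remove it, because none of those endpoints answers the duration question in 2.2.6.

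The item 7 effect is also modest and noisy. With 20 to 60 baseline-5 patients per arm (assumed), the difference in medians under step 3 has a sampling SD of about 2.5 to 1.5 days, against a true gap of 0.7. In whole days, rounded up, the control median is strictly lower in only 57% to 60% of simulated trials. That also stands: the reversal is possible, not general.

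A reader might infer that item 8 reverses as item 7 does. A calculation in which only deaths differ seems to show it: off oxygen 0.08/day, death 0.02 vs 0.01, medians ln 2/0.10 = 6.9 vs ln 2/0.09 = 7.7. That needs deaths to differ without a matching difference in intubation. The item 8 definition counts ventilated days, and step 5 shows near-equal medians when both differ.

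**Conclusion.** The point holds for item 7: intubation and death are both recorded as a shorter duration, and the only planned summary for objective 2.2.6 can favour the arm with more of them. This follows from the definitions at equal recovery. The size rests on assumed hazards: about 5.3 vs 6.0 days in the main case, gone at about 15% better recovery. Item 6 has the weaker form, through death alone. Item 8 is truncated by death but does not reverse materially under the item 7 scenarios. The documents do not support a reading in which all three durations mislead, or in which the trial's main efficacy conclusion is at risk. The change is worth making, but the consequence is limited.

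**What to change.** For objective 2.2.6, add days alive and free of the support through Day 28:

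- **Thresholds:** score below 6, below 5 and below 4 for the three kinds of support, so that higher support counts as not free. Patients who die by Day 28 get 0.
- **Analysis set:** all randomised patients who received at least one dose. The exclusion in section 13.4 of patients without Day 28 data should not carry over.
- **Missing scores:** for loss or withdrawal, carry the last observed score forward to Day 28 against the same thresholds, so a patient lost while intubated is not free. Add a sensitivity analysis.
- **Comparison:** a Wilcoxon test stratified by age and severity, with any baseline 6-7 patients in the severe stratum. Label it secondary and unadjusted for multiplicity, and show it beside mortality.
- **Items 6 to 8:** keep them as descriptive, labelled as conditional on baseline support and truncated by death, with item 7 also interrupted by intubation.

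Under step 3 the new item 7 measure has medians of 19.1 control vs 20.3 drug, and with faster extubation 19.7 vs 20.4, so it points the right way in both.

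The composite has costs. It mixes death with duration, ventilator-free days may pile up at the maximum, and its direction is not guaranteed. If intubated patients moved straight below score 5 at 0.15/day, faster than the 0.10/day from score 5, its medians would be 21.3 control vs 21.2 drug.

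It needs the same Day 1 to 28 daily scores as items 6 to 8, so if those exist the change is SAP wording only. Section 12.0 implies that they do: "The ordinal scale used for assessment of the clinical and respiratory status on each day of the study is included below". The schedule in section 4.0 has no column for Days 15 to 27, however, and sections 10.2 to 10.4 move deteriorating patients to follow-up at Days 28 and 56 and end follow-up for alternative therapy. Those sections must be reconciled. That is a separate point, as is the restriction of items 6 to 8 to patients already on the support at baseline.
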